### **9.1.2 Acneiform rash**

The severity of acneiform rash is graded according to the NCI-CTCAE, Version 3.0, definition of rash/desquamation.

Based on emerging data, there appears to be a correlation between acneiform rash and various efficacy outcomes. Therefore, if a patient experiences a grade 1 - 3 acneiform rash, cetuximab therapy may continue without dose modification or delay. The investigator could consider concomitant treatment with topical and/or oral antibiotics.

### **9.1.3 Hematologic toxicities**

Hematologic toxicity is not an expected toxicity associated with cetuximab.

### **9.1.4 Nonhematologic toxicities**

Guidelines for cetuximab dose modification related to nonhematologic toxicity may be found in Section 10.1.

### **9.1.5 Electrolyte monitoring**

In 244 patients evaluated in ongoing, controlled clinical trials, the incidence of hypomagnesemia, both overall and severe (NCI-CTCAE Version 3.0 grades 3 and 4), was increased in patients receiving cetuximab alone or in combination with

chemotherapy as compared to those receiving best supportive care or chemotherapy alone. Approximately one-half of these patients receiving cetuximab experienced hypomagnesemia and 10-15% experienced severe hypomagnesemia. The onset of electrolyte abnormalities has been reported to occur from days to months after initiation of cetuximab. Electrolyte repletion was necessary in some patients and in severe cases, intravenous replacement was required. The time to resolution of electrolyte abnormalities is not well known.

## **9.2 IMC-A12**

Adverse events of concern, which may or may not be associated with IMC-A12 therapy, include infusion reactions, hyperglycemia, and peri-operative complications.

### **9.2.1 IMC-A12 infusion reactions**

IMC-A12 infusion reactions will be defined according to the NCI-CTCAE Version 3.0 definition of allergic reaction/hypersensitivity, as detailed below. Consistent with usual medical practice, selected parenteral medications may be utilized for grade 2 allergic/hypersensitivity reaction as detailed below. The Eli Lilly & Co. Medical Monitor should be contacted immediately if questions arise concerning the grade of the reaction.

- Grade 1: transient flushing or rash, drug fever <38°C
  - ✓ Treatment: Slow infusion rate by 50% and monitor patient for worsening of condition.
- Grade 2: rash, flushing, urticaria, dyspnea, drug fever ≥38°C
  - ✓ Treatment: Stop the infusion, administer diphenhydramine hydrochloride 50 mg i.v., acetaminophen 650 mg orally for fever, and oxygen. Resume infusion at 50% of the prior rate once the infusion reaction has resolved or decreased to grade 1; infusion duration should not exceed 2 hours. Monitor patient for worsening condition, and premedicate with diphenhydramine hydrochloride 50 mg i.v. for subsequent infusions.

- ✓ For a second grade 1 or 2 infusion reaction, administer dexamethasone 10 mg i.v.; for subsequent infusions, premedicate with diphenhydramine hydrochloride 50 mg i.v., acetaminophen 650 mg orally, and dexamethasone 10 mg i.v. (or equivalent).
- Grade 3: symptomatic bronchospasm, requiring parenteral medication(s), with or without urticaria; allergy-related edema/angioedema, hypotension

✓ Treatment: Stop the infusion and disconnect infusion tubing from the patient. Administer diphenhydramine hydrochloride 50 mg i.v., dexamethasone 10 mg i.v. (or equivalent), bronchodilators for bronchospasms, and other medications/treatment as medically indicated. Patients who have a grade 3 infusion reaction will not receive further IMC-A12 or cetuximab treatment, but will continue to be followed on the protocol.

- Grade 4: anaphylaxis (a life-threatening event characterized by the rapid onset [often within minutes] of airway obstruction [bronchospasm, stridor, hoarseness], urticaria, and/or hypotension)

✓ Treatment: stop the infusion and disconnect the infusion tubing from the patient. Administer diphenhydramine hydrochloride 50 mg i.v., dexamethasone 10 mg i.v. (or equivalent), and other medications/treatment as medically indicated. Epinephrine or bronchodilators should be administered as indicated. Hospital admission for observation may be indicated. Patients who have a grade 4 infusion reaction will not receive further IMC-A12 or cetuximab treatment, but will continue to be followed on the protocol.

### **9.2.2 Hyperglycemia (Diabetes)**

For the assessment of hyperglycemia (diabetes), both the NCI-CTCAE Version 3.0 Endocrine (pancreatic endocrine: glucose intolerance / diabetes) and Metabolic / Laboratory (glucose, serum-high / hyperglycemia) terms should be used. If hyperglycemia/diabetes occurs during treatment with IMC-A12, treatment is dependent upon symptom severity. For grade 1 or 2 hyperglycemia (fasting glucose < 250 mg/dL),

IMC-A12 treatment should continue; oral agents or insulin may be used as clinically indicated.

For grade 3 hyperglycemia (fasting glucose 250-500 mg/dL), IMC-A12 treatment may continue if the patient is asymptomatic and glucose < 300mg/dL; insulin may be initiated. IMC-A12 and cetuximab should be discontinued for grade 3 hyperglycemia if there are symptoms interfering with ADL or if glucose is  $\geq$  300mg/dL

For grade 4 hyperglycemia (fasting glucose >500 mg/dL), IMC-A12 and cetuximab therapy should be discontinued.

### **9.2.3 Peri-operative complications**

Cetuximab has not been studied pre-operatively in patients with HNSCC. However, preliminary reports of two studies of cetuximab in combination with chemotherapy prior to liver resection in patients with metastatic colorectal cancer did not raise post-operative toxicity concerns. IMC-A12 has never been studied in the pre-operative setting. Although there is no pre-clinical data that suggests an increased incidence of peri-operative complications with IMC-A12, patients will be closely monitored for these adverse events. In case a higher than expected incidence of peri-operative complications is seen, considerations will be given to terminating the study, or modifying the protocol, so as to increase the interval between the last dose of the study drug(s) and the surgical procedure.

## **10 Dose modifications and study completion**

### **10.1 Dose modifications**

Dose reductions of either cetuximab or IMC-A12 are not permitted. However, treatment with both drugs may be delayed according to the following guidelines:

- For grade 1, no dose delay is required.

- Patients with any grade 2 adverse event may, at the investigator's discretion, continue to receive study drugs(s) per protocol provided that the event does not pose a serious health risk or is easily treated.
- For a grade 3 clinically significant toxicity (excluding fatigue, skin rash and hyperglycemia/diabetes) not adequately controlled with appropriate supportive care, discontinue treatment. For grade 3 toxicity not considered to be clinically significant by the investigator, withhold dose until toxicity is  $\leq$  grade 1 or has returned to pretreatment baseline, then resume treatment with the protocol-planned dose.
- For a grade 4 possible, probable or definite treatment-related toxicity, discontinue treatment.

The above are considered general guidelines. The investigator should use his or her best judgment when determining treatment interruptions. For example, some grade 2 non-hematologic toxicities may require treatment delays, and some grade 3 or 4 organ toxicities (e.g., hepatic, renal, cardiac, central nervous system) may require a permanent discontinuation from the investigational treatment.

If cetuximab administration is interrupted, no re-bolus dose should be administered at the time of treatment resumption (i.e., subsequent dose of cetuximab will be 250 mg/m^2). In arm C, if cetuximab treatment needs to be delayed or discontinued due to toxicity, so will treatment with A-12. Similarly, in arm C, if IMC-A12 treatment needs to be delayed or discontinued due to toxicity, so will treatment with cetuximab.

## **10.2 Removal of patients from therapy**

A patient should be withdrawn from therapy if, in the opinion of the investigator, it is medically necessary, or if it is the wish of the patient. If the patient does not return for a scheduled visit, every effort should be made to contact the patient; in any circumstance, patient outcome should be documented whenever possible.

A patient should be removed from therapy if:

- Tumor progression occurs, and is confirmed by radiographic progression (not solely based on clinical and/or tumor marker suggestions of progression, unless global deterioration of health status (symptomatic deterioration) requiring discontinuation occurs);
- A grade 4 possible, probable or definite treatment-related toxicity occurs;
- There is toxicity requiring more than 7 days delay of the second treatment dose;
- Other unacceptable toxicity necessitates cessation of treatment;
- The physician feels it is in the best interest of the patient to stop the treatment;
- The patient requests to be removed from the study;
- The patient is lost to follow-up;
- The patient becomes pregnant, or
- The sponsor (MDACC), supporting drug companies (Eli Lilly & Co. and ImClone Systems) or investigator terminates the study.

### **10.3 *Study completion***

This study will be considered complete when one or more of the following conditions is met:

- All patients have completed all required study visits.
- All patients have discontinued from the study.
- The IRB, Eli Lilly & Co., or ImClone Systems discontinues the study because of safety considerations.

Long-term efficacy and toxicity data may continue to be collected after the study has been completed.

## 11 Criteria for tumor response evaluation

### 11.1 *Clinical response*

Patients will be evaluated for response according to the Response Evaluation Criteria in Solid Tumors (RECIST) guidelines. Additionally, waterfall plots will be used to depict changes in post-treatment tumor size from baseline. There will be no confirmatory scans after a response has been documented, since patients are expected to have the tumor resected shortly after the imaging studies.

#### 11.1.1 Baseline tumor assessment

The baseline tumor burden (unidimensionally-measurable and nonmeasurable disease) will be assessed as closely as possible to the beginning of treatment. The investigator will prospectively identify the lesions to be followed to evaluate the patient's response to therapy (see Section 11.1.4, Definitions of Response).

#### 11.1.2 Method of tumor response assessment

All measurements should be taken and recorded in metric notation, using a ruler or calipers according to RECIST guidelines and documented on patient's medical record. Tumor measurements will be done by PI or collaborator.

The same method of assessment and the same technique should be used to characterize each identified and reported lesion at baseline and at reassessment during treatment. Imaging-based evaluation will be preferred to evaluation by clinical examination when both methods have been used to assess the antitumor effect of a treatment. Lesions evaluated clinically will only be considered measurable when they are superficial (eg, skin nodules, palpable lymph nodes). CT and MRI will be considered the best currently available and reproducible methods to measure target lesions (as defined in Section 11.1.4).

### **11.1.3 Definitions**

Measurable lesions:

Lesions that can be accurately measured in at least one dimension (longest diameter to be recorded) as > 2 cm with conventional techniques or as > 1 cm with spiral CT scan.

A lesion located in a previously irradiated area will be considered measurable only if there has been a documented increase in its size subsequent to irradiation but prior to study entry.

Non-measurable lesions:

All other lesions including small lesions (longest diameter < 2 cm with conventional techniques or < 1 cm with spiral CT scan) and truly non-measurable lesions.

Lesions considered to be truly non-measurable include the following: bone lesions; ascites; pleural/pericardial effusion; inflammatory breast disease; lymphangitis cutis/pulmonis; abdominal masses that are not confirmed and followed by imaging techniques; and cystic lesions..

### **11.1.4 Definitions of response**

Overall tumor response, as defined in the Criteria for Overall Response Table, will be based on an integration of the evaluation of target, non-target, and new lesions, as described below:

Target lesions:

Target lesions are all measurable lesions up to a maximum of five lesions per organ and 10 lesions in total, representative of all involved organs. Target lesions should be selected on the basis of their size (those with the longest diameters) and their suitability for accurate repeated measurements.

The sum of the longest diameters of all target lesions will be calculated at baseline and reported as the baseline sum longest diameter (LD). This baseline sum LD will be used

as the reference by which to characterize the objective tumor response. For lesions measurable in two or three dimensions, always report the longest diameter at the time of each assessment.

Complete Response (CR): The disappearance of all target lesions.

Partial Response (PR): At least a 30% decrease in the sum of the longest diameters of target lesions, taking as reference the baseline sum LD.

Stable Disease (SD): Neither sufficient shrinkage to qualify for partial response nor sufficient increase to qualify progressive disease, taking as reference the smallest sum LD since the treatment started.

Progressive Disease (PD): At least a 20% increase in the sum of the LD of target lesions, taking as reference the smallest sum longest diameter recorded since the treatment started or the appearance of one or more new lesion(s).

#### Non-target lesions

All lesions (or sites of disease) not characterized as target lesions, both measurable and nonmeasurable, will be identified as non-target lesions and will be recorded at baseline. Measurements will not be required, and these lesions will be followed as “present” or “absent.”

Complete Response (CR): The disappearance of all non-target lesions and the normalization of the tumor marker level (if tumor markers are measured and are initially above the upper limit of normal, those must normalize for a patient to be considered in complete clinical response).

Stable Disease (SD): The persistence of one or more non-target lesions and/or the maintenance of the tumor marker level above normal limits.

Progressive Disease (PD): The appearance of one or more new lesions and/or unequivocal progression of existing non-target lesions. Because the clear isolated progression of non-target lesions is exceptional, in such circumstances, the opinion of the treating physician should prevail.

### **11.1.5 Determination of overall clinical response**

Each response parameter (target, non-target, and new lesions) will be reported independently at each radiologic read. The investigator will make a determination of overall response based on the evaluation of target, non-target, and new lesions, as shown in the Criteria for Overall Response Table below.

Criteria for Overall Response Table

Target Lesions	Non-Target Lesions	New Lesions	Overall Response
CR	CR	No	CR
CR	SD	No	PR
PR	Non-PD	No	PR
SD	Non-PD	No	SD
PD	Any	Yes or No	PD
Any	PD	Yes or No	PD
Any	Any	Yes	PD

### **11.2 Histopathological changes**

Changes in histologic parameters in the post-treatment surgical specimen will be evaluated both in the tumor and in the host tissue, using a scoring system of 0, 1, 2, and 3 (0, 0-25%, 26-50%, more than 50% of the tissue showing the feature, respectively), or a binary system (positive or negative).

### **11.2.1 Tumor tissue**

The features to be evaluated in the tumor tissue include: necrosis, dyskeratosis, keratinization, and apoptosis (all using the 0-3 scoring system).

### **11.2.2 Host tissue**

The features to be evaluated in the host tissue include: fibrosis (using the 0-3 scoring system), immune response (binary system, accompanied by a description of the types of inflammatory cells involved), granulomatous inflammation (binary system), dystrophic features (binary system), and angiogenesis (binary system classifying as high or low).

## **12 Planned statistical method**

### **12.1 Primary endpoint**

The primary endpoint of this trial is the modulation of phospho-Akt in the post-treatment, surgical tumor specimen as compared to the baseline tumor specimen in the different treatment groups. Levels of phospho-Akt will be determined by IHC as described in section 6.9.1.

### **12.2 Secondary endpoints**

#### **12.2.1 Tissue- and blood-based biomarkers**

Since there is no standard for determination of molecular activity of either cetuximab or IMC-A12, biomarkers in tumor tissue specimens and blood will be evaluated in an exploratory fashion so as to identify changes from baseline and differences between the two study arms and correlate them with other efficacy and toxicity outcomes. Biomarkers involved in intermediary metabolism will be evaluated in the blood and in the post-treatment specimens of skeletal muscle and adipose tissue in an exploratory fashion so as to identify differences between the two study arms and correlate them with toxicity outcomes.

Blood-based biomarkers will be evaluated in [name] laboratory. Tumor tissue-based biomarkers will be evaluated in the laboratories of Drs. [name] , [name] and [name].

Tumor-tissue based biomarkers will include (but are not restricted to): IGF-1R, phospho-IGF-1R, IGF-2R, IGF-1, IGF-2, IGFBP-3, EGFR, phospho-EGFR, survivin, Ki-67, caspase-3, HIF-1 alpha, CD31, MMP-2, MMP-9, phosphorylation status of multiple kinases (using antibody arrays), micro-RNA and messenger-RNA expression levels (using high-throughput microarray chips), high-throughput proteomic analysis, genomic analysis and other biomarkers that may emerge to be important related to the use of EGFR and/or IGF-1R-targeted therapy.

Skeletal muscle and adipose tissue-based biomarkers will include (but are not restricted to): insulin receptor, phosphorylated insulin receptor (phospho-tyrosine and phospho-serine), insulin receptor substrate-1 (phospho-tyrosine and phospho-serine) and its downstream effectors, glucose transporter-1, glucose transporter-4, hexokinase, PPAR-alpha, PPAR-gamma, phosphorylation status of multiple kinases (using antibody arrays), micro-RNA and messenger-RNA expression levels (using high-throughput microarray chips), high-throughput proteomic analysis, genomic analysis and other biomarkers that may emerge to be important for anti-IGF-1R therapy-induced toxicity.

Blood-based biomarkers will include (but are not restricted to): free and total IGF-1 and IGF-2, IGFBP-3, insulin, peptide C, free fatty acids, triglycerides, fructosamine, a panel of 59 cytokine and angiogenic factors measured by available luminex multiplex beads kits (Bio-Plex 27-Plex & 23-Plex Kits [Bio-Rad, Hercules, CA] and Human CVD Biomarker Panel 1 kit [Linco Research, Inc., St, Charles, MO]), VEGF, solubleVEGFR-1, soluble VEGFR-2, osteopontin, high-throughput proteomic analysis, genomic analysis and other biomarkers that may emerge to be important for characterization of cetuximab and/or IMC-A12 activity and/or toxicity.

### **12.2.2 Objective response to treatment**

RECIST guidelines and waterfall plots will be used to describe the objective response to treatment in each arm.

### **12.2.3 Histopathological changes after treatment**

Tumor tissue changes: necrosis, dyskeratosis, keratinization, and apoptosis

Host tissue changes: fibrosis, immune response, granulomatous inflammation, dystrophic features, and angiogenesis.

### **12.2.4 Safety**

The toxicity associated with each treatment arm will be observed and characterized; toxicity will be reported by type, frequency, and severity, as determined in section 8.

## **12.3 Analysis population**

Analysis of the primary endpoint will be performed only in the evaluable population.

Toxicity endpoints will be analyzed in the safety population.

Populations:

- Evaluable population: will comprise all randomized patients who receive at least one dose of the study drug(s) in this trial, based on the arm to which they were randomized. Additionally, the last treatment dose should have been administered within 10 days of the surgical resection. The evaluable population will only include patients whose both baseline and post-treatment tumor tissue samples are successfully analyzed for phospho-Akt levels. The reasons for non-evaluability in each arm will be assessed, at the time of the final analysis.
- Safety population: will include all patients who received any dose of an investigational product. The patients will be analyzed for product safety as part of the treatment actually received, regardless of which treatment they were randomized to receive.

For the studies involving assessment of intermediary metabolism parameters, arms B and C may be combined and compared / contrasted to arm A.

## **12.5 Statistical analysis**

Modulation of phospho-Akt (difference in IHC score between the surgical specimen and the baseline biopsy) and other biomarkers will be compared between any two of the three treatment arms with the use of Wilcoxon rank sum test. Further evaluations will adjust

comparisons of follow-up marker values for baseline values, when available, using analysis of covariance. Prior to analysis by parametric methods (such as analysis of covariance), we will assess the data for the need for transformation to normality, transforming where appropriate. We will use repeated measures analysis of variance to analyze endpoints that are observed at multiple time points (e.g. serum glucose). Spearman's rank correlation test will be used to investigate the relationship between different biomarkers and between biomarkers and toxicity. Correlations of categorical variables will be assessed by Fisher's exact test. A type I error rate of 0.05 (two-sided test) will be used for all comparisons.

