### **1.3.2.1 Hyperglycemia**

Hyperglycemia was the most common adverse event in the CP13-0501 trial (4 patients) and the only grade  $\geq 3$  toxicity (2 patients) observed. Three patients had a better characterization of hyperglycemia. Although known diabetes was an exclusion criteria for participation in the trial, all 3 patients with hyperglycemia had evidence of pre-existing glucose intolerance prior to initiation of the study on retrospective chart review. Increases in blood glucose levels occurred soon after the first dose (in 2 patients), were in the range of 350 mg/dL, and responded to oral hypoglycemic agents (glipizide or glyburide, and/or metformin).

In a phase II trial of another anti-IGF1-R antibody (CP-751,871) given in combination with carboplatin and paclitaxel to 48 patients with lung cancer, grades 3-4 hyperglycemia occurred in 20% of patients (10% grade 3, 10% grade 4). However, there is no published data on further characterization of these hyperglycemic episodes, nor a detailed study of the pathophysiologic processes involved in this adverse event.

Anti-IGF-1R-induced hyperglycemia might occur due to peripheral impaired glucose metabolism or decreased insulin secretion. IGF-1 has hypoglycemic effects *in vivo* in humans, which are thought to be mediated by the IGF-1R in adipose tissue and skeletal muscle and by the IR in the liver (since adults do not express IGF-1R in hepatocytes). In adipose tissue, IGF-1 induces pre-adipocyte differentiation into adipocytes by a mechanism involving PPAR-gamma, whereas in skeletal muscle, IGF-1R activation leads to increased GLUT-4 mediated glucose uptake. In the liver, IGF-1 has been shown to

decrease hepatic glucose production. The role of IGF-1R signaling in insulin production by pancreatic beta-cells has also been recently characterized: both the presence of IR and IGF-1R (and their hybrid receptors) in these cells seems to be necessary for adequate insulin secretion. IGF-1R also seems to play a major role in pancreatic beta-cells survival in the long term.

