## **3.5 *Methods for assigning patients to treatment groups***

Patients will be stratified according to the primary site of the head and neck cancer (i.e., non-skin primary or skin primary), and the current use of any anti-hyperglycemic pharmacologic agent and will be then randomly assigned 1:1:1 to one of the three treatment groups:

Arm A: cetuximab alone

Arm B: IMC-A12 alone

Arm C: cetuximab + IMC-A12

Patients will be assigned to each treatment arm by M. D. Anderson's computer-based CORE system. The randomization code will be generated by the study biostatistician and stored in the CORE database prior to initiation of the trial. The investigators will be

blinded to the code. Since we have two stratification factors, four sets of codes (one for each strata) will be produced. Random permuted block design with a block size of 3 or 6 will be used within each one of the four strata.

Since there is limited data on the use of IMC-A12 in diabetic patients, as added precautions, if toxicity data on this study and on the randomized phase II conducted at M. D. Anderson in the setting of platin-refractory recurrent HNSCC raise concern about including diabetic patients, additional considerations will be made to include diabetes as an exclusion criteria and, as a result, stratification of patients according to the use of anti-hyperglycemic pharmacologic agent will no longer be performed.

After enrollment, patients will be assigned a unique study identification number and cohort. The study identification number and the patient's initials will be recorded on PDMS and/or CORE databases and correspondence regarding the patient.

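### Section 12.5 analyses glucose and other metabolic markers without the two randomisation factors and without separating values drawn after glucose-lowering treatment starts

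*Combined protocol and SAP*

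**What the plan says.** Section 12.5 gives one sentence to serial metabolic data: "We will use repeated measures analysis of variance to analyze endpoints that are observed at multiple time points (e.g. serum glucose". Separately, it plans to adjust "comparisons of follow-up marker values for baseline values, when available, using analysis of covariance". The marker's own baseline is the only covariate named anywhere in Section 12.

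Section 3.5 stratifies randomisation on primary site (skin or non-skin) and on "the current use of any anti-hyperglycemic pharmacologic agent", with permuted blocks in each of the four strata. It also allows the drug-use stratum to be discontinued if patients with diabetes are later excluded.

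Section 9.2.2 sets out what happens when glucose rises. For grade 1 or 2, "IMC-A12 treatment should continue; oral agents or insulin may be used as clinically indicated". For asymptomatic grade 3 below 300 mg/dL, IMC-A12 may also continue and "insulin may be initiated". At 300 mg/dL or above, with symptoms that interfere with daily activities, or at grade 4, both antibodies are stopped.

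Section 2.2 makes the effect of IMC-A12 on glucose metabolism the second secondary objective. Section 1.4.5 says insulin and peptide C are measured to judge insulin secretion and resistance. Section 6.2 keeps concurrent medications out of the CRF. Section 8.5 does capture the treatment given for each adverse event.

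**The concern.** There are two gaps. First, randomisation is stratified on a factor that bears directly on glucose, insulin and peptide C, but no analysis uses it. The reported error then includes variation that the design has already balanced across arms.

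Second, glucose-lowering treatment started on study is itself a consequence of the effect being studied. It should fall mainly in arms B and C: the Section 9.2.2 rules sit under IMC-A12, and the adverse events that Section 9.1 lists for cetuximab do not include hyperglycemia. Section 1.3.2.1 reports that rises in the phase I trial "were in the range of 350 mg/dL, and responded to oral hypoglycemic agents". A patient with a large rise who is treated may therefore contribute a much lower value at the next draw.

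The plan does not say whether it wants the effect of IMC-A12 with permitted treatment included or the drug's own effect. The objective stresses the pathophysiology of hyperglycemia, which points towards the latter. Insulin has a sharper problem, because a sample taken after injected insulin can be misread as increased secretion. Section 1.3.2.1 lists the effect of IGF-1R blockade on secretion as an open question.

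**Working it through.** **1. The plan's own figure.** Section 12.4 sizes the trial on phospho-Akt only; nothing is sized on glucose. The figure reproduces:
- Φ(1.5/√2) = 0.856.
- With two-sided 0.05/3 per pair, Noether's formula gives total N = (2.394 + 1.282)² / (3 × 0.356²) = 13.51 / 0.380 = 35.5. That is 17.8 per arm, so 18, and 18 / 0.90 = 20.

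The present point does not touch this.

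**2. Stratum term.** The documents give no share of patients on anti-hyperglycemic drugs and no glucose SD. Assume a share q of 5 to 30% and a stratum difference d of 0.25 to 1.0 residual SD. The standard error without the term, relative to that with it, is √(1 + q(1−q)d²).

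| q | d | q(1−q)d² | SE ratio |
|---|---|---|---|
| 0.05 | 0.25 | 0.0030 | 1.001 |
| 0.20 | 0.50 | 0.040 | 1.020 |
| 0.30 | 1.00 | 0.21 | 1.100 |

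The standard error is therefore about 0.1 to 10% too large. This applies to between-patient comparisons of level. A constant stratum shift does not enter the within-patient error used for the arm-by-time contrast, and baseline adjustment absorbs part of it elsewhere. The effect of primary site on glucose was not quantified.

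**3. Can a draw follow rescue?** Doses are nominally on days −9 and −2 (Section 4.1). The chemistry profile is taken at baseline, within 5 days before dose 2 (and dose 3 if given), and on the day of surgery or up to 2 days before (Section 7.5). Stored blood is also taken within 30 days after surgery (Section 6.10.3). In phase I, rises came soon after the first dose in 2 patients (Section 1.3.2.1). Later draws can therefore follow rescue, but the pre-dose-2 draw may precede it.

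**4. Size of the rescue effect, for illustration only.** Let r be the fraction of IMC-A12 patients rescued, with none in arm A. Let E be their unrescued excess, m the rise in the other IMC-A12 patients, and f the fraction of E that rescue removes.
- Unrescued difference = rE + (1−r)m
- Observed difference = rE(1−f) + (1−r)m
- Shrinkage = rEf / [rE + (1−r)m]

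All inputs are assumed for this trial. r is 10%, 19% (4/21, the phase I frequency in the Synopsis) or 25%. E is 240 mg/dL (350 minus an assumed usual 110) or a milder 120.

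| E (mg/dL) | m (mg/dL) | f | Shrinkage over r = 10 to 25% |
|---|---|---|---|
| 240 | 5 to 20 | 50% | 29 to 47% |
| 240 | 5 to 20 | 100% | 57 to 94% |
| 120 | 10 | 25% | 14 to 20% |
| 120 | 10 | 50% | 29 to 40% |

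Example with r = 4/21, E = 240, m = 5, f = 50%: unrescued 45.7 + 4.0 = 49.8 (from unrounded terms); observed 22.9 + 4.0 = 26.9; shrinkage 46%. If only the second of two post-dose draws follows rescue, the average is (49.8 + 26.9)/2 = 38.4, a shrinkage of 23%. If nobody is rescued before a draw, it is zero.

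**5. Spread.** In simulation (40 patients in B and C against 20 in A, residual SD 20 assumed, r = 4/21, E = 240, m = 10, f = 50%), the SD of the estimated difference fell from 15.2 to 8.7 mg/dL with rescue. Rescue moves the estimate relative to a no-rescue target; it does not widen it.

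**The case against.** The strongest reply is that observed values are the right data if the target is the effect of IMC-A12 under the management the protocol allows. That is correct. The bias exists only for a no-rescue target, and the plan names neither. What stands is the need to say which is meant and to show the other.

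A reader might go further and infer that the IMC-A12 effect will be mostly erased. Putting all 4 of 21 phase I patients at 350 mg/dL, with rescue to 150 to 200, gives a loss of (350−200)/240 = 63% to (350−150)/240 = 83%. The documents do not support that.
- Only 2 of the 4 patients had grade 3 or worse. If the other two lay between 110 and 250 mg/dL, the mean excess is (2/21) × 240 = 22.9 up to 22.9 + (2/21) × 140 = 36.2 mg/dL, against 45.7 with all four at 350.
- Section 9.2.2 stops both antibodies at 300 mg/dL, so rescue with IMC-A12 continuing at 350 is not a protocol scenario.
- Phase I excluded known diabetes. This trial admits it on a stable regimen but requires fasting glucose below 130 mg/dL. Neither the rate nor the size carries over.

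A reader might also infer that the stratification is wasted. It is not: the blocks still balance the factor, and the cost is the modest loss of precision shown above.

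It is also fair to say that the analyses are exploratory and that the safety signal survives, since hyperglycemia is graded and reported as an adverse event. Peptide C, already collected, partly covers the insulin question. None of this tells the analyst what to do with a post-rescue glucose or insulin value.

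**Conclusion.** Both omissions are real and sit in the analysis of a named secondary objective. The missing stratum term costs about 0.1 to 10% in the between-patient standard error, given 5 to 30% of patients on background drugs and a stratum difference of 0.25 to 1.0 SD.

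The missing rescue rule matters more, but its size cannot be fixed from the documents. Shrinkage ranges from zero to most of the difference, depending on how many patients are rescued before a draw and how well they respond, and it is a bias only if the target is the drug's own effect. That post-injection insulin values do not measure secretion needs no such assumption about size.

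That glucose will be analysed as observed is the natural default from the plan's silence, not something it states. This is a worthwhile clarification at low cost, not a threat to the trial's primary result.

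**What to change.** Amend Section 12.5 before the data are analysed:

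1. Include both randomisation factors and the marker's baseline value in the ANCOVA and repeated measures models for metabolic markers. Drop the drug-use term if that stratum is discontinued under Section 3.5.
2. Keep the observed-value analysis as main and state that it estimates the effect with permitted treatment included. Add a sensitivity analysis that replaces values after the start or increase of glucose-lowering treatment with the last pre-rescue value, or with a worst rank. Worst ranks should not be the main analysis: the study is open-label and rescue is discretionary, so they could exaggerate the difference. Report rescue by arm.
3. Exclude insulin values taken after exogenous insulin from the secretion analysis and rely on peptide C there, noting that given insulin can also lower peptide C.

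Take the type and start date of rescue from the adverse-event treatment record and the medical record, because the CRF does not hold concurrent medications. The strata are already recorded at randomisation. The cost is some chart abstraction and one additional analysis. No rescue, dosing or eligibility rule changes.
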